**Table 5. Derivation of “Each Day” and “Any Day” for Local Reactions in the Presence of Missing Values**

Subject	Day	Response	Each Day	Any Day
1	1	Missing	Missing	
	2	No	No	
	3	Yes	Yes	
	4	No	No	Yes

**Table 5. Derivation of “Each Day” and “Any Day” for Local Reactions in the Presence of Missing Values**

Subject	Day	Response	Each Day	Any Day
2	1	No	No	
	2	Yes	Yes	
	3	Missing	Missing	
	4	No	No	Yes
3	1	No	No	
	2	Missing	Missing	
	3	No	No	
	4	No	No	Missing
4	1	No	No	
	2	No	No	
	3	No	No	
	4	No	No	No

Note: These are examples of derivations. The electronic diary will contain data for 7 days.

For “any local reaction” on a given day, a similar rule applies:

=1 (yes), if the subject reports any reaction as yes (or present) on the given day in the required interval.

=0 (no), if the subject reports all reactions as no (or absent) on the given day in the required interval.

= missing, if the subject reports all reactions as a combination of no and missing on the given day in the required interval.

For “any local reaction on any day,” a similar rule applies:

=1 (yes), if the subject reports any reaction as yes (or present) on any day in the required interval.

=0 (no), if the subject reports all reactions as no (or absent) for all days in the required interval.

= missing, if the subject reports all reactions as a combination of no and missing.

In summarizing local reactions (over all expected days), the derivation of “any reaction” in the presence of missing values is depicted in [Table 6](#).

**Table 6. Derivation of Any Reaction for Local Reactions in the Presence of Missing Values**

Number of Reactions Reported	Number of Missing Values	Summary Value
One or more	None	Reaction
One or more	One or more	Reaction
None	None	No reaction
None	One or more	Missing

The duration of each reaction will be calculated in days from the start of the first reported reaction to resolution of the last reported reaction, inclusive, ie, end date – start date + 1. Resolution information is the last day on which the report was recorded in the e-diary, or the date the reaction ended if it continued beyond Day 7 (or the last record in the e-diary if before Day 7). If there is no known date on which the reaction ended, then duration will be missing. Subjects with no reported reaction have no duration because it is not applicable.

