6.1.1.2. Visit 2 (28 to 42 Days After Visit 1)

- Review the subject's e-diary data and follow up on any ongoing local reactions or systemic events.
- Based on clinical evaluation, determine whether any AEs or SAEs have occurred since the last study visit and record them on the CRF.

- Review AEs that were ongoing from the previous visit and record their end dates or confirm that they are still ongoing.
- Ensure that the subject continues to be eligible for the study and meets none of the withdrawal criteria ([Section 6.2](#)).
- On the day of vaccination, prior to vaccination, measure and record the subject's axillary temperature.
- Ensure that the subject does not meet any of the temporary delay criteria ([Section 4.3](#)).
- An appropriate site staff member will use the IRT system to obtain the subject's investigational product DU or container number.
- Administer a single 0.5-mL intramuscular injection of 13vPnC from an MDV or a PFS into the anterolateral thigh muscle of the left leg.
- Administer a single intramuscular dose of DTP-Hib-HBV into a different limb from that used to administer 13vPnC, according to local clinical practice.
- Administer a single dose of rotavirus vaccine according to local clinical practice.
- Observe the subject for at least 30 minutes after vaccination for any significant acute reactions. Any AE noted during the observation period should be recorded on the source documents and on the AE section of the CRF.
- Issue a caliper and a digital thermometer (if necessary) to the parent(s)/legal guardian(s)/caregiver(s) and provide instructions on their use.
- Issue a subject e-diary (if necessary) to the parent(s)/legal guardian(s)/caregiver(s). Provide instruction on its completion for 7 days (Day 1 through Day 7, where Day 1 is the day of vaccination).
- Ask the parent(s)/legal guardian(s)/caregiver(s) to contact the investigator immediately if any significant illness or hospitalization occurs during the study period, or if the subject experiences a large (>14 caliper units) local reaction.
- Schedule an appointment with the parent(s)/legal guardian(s)/caregiver(s) for the next study visit.
- Remind the parent(s)/legal guardian(s)/caregiver(s) to bring the e-diary to the next study visit.
- The investigator or an authorized designee completes the source documents, completes the CRF, and updates the investigational product accountability records.

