7.1.1. Electronic Diary

Subject's parent(s)/legal guardian(s)/caregiver(s) will be required to use an e-diary, based on appropriate technology, and will be asked to monitor and record local reactions and systemic events for 7 days following vaccination (Day 1 through Day 7, where Day 1 is the day of vaccination). The e-diary allows recording of these assessments only within a fixed time window, thus providing the accurate representation of the subject's experience at that time. Local reactions and systemic events will be collected in the e-diary in the evening daily during the e-diary reporting period.

Data on local reactions and systemic events reported on the e-diary will be transferred electronically to a third-party vendor, where they will be available for review by investigators and the Pfizer clinicians at all times via an internet-based portal.

At intervals agreed to by the vendor and Pfizer, these data will be transferred electronically into Pfizer's database for analysis and reporting. These data do not need to be reported by the investigator in the CRF as AEs.

Investigators (or appropriately qualified designee) are required to review the e-diary data online at frequent intervals as part of the ongoing safety review. The investigator or designee must contact the subject's parent(s)/legal guardian(s)/caregiver(s) in order to obtain stop dates for any ongoing local reactions or systemic events on the last day that the e-diary was completed. The stop dates should be documented in the source documents and the information entered in the CRF.

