### 3.5.2.2.2. Fever

The subject's axillary temperature will be recorded in the e-diary for 7 days (Day 1 to Day 7) after each vaccination. The protocol defines fever as a temperature  $\geq 38.0^{\circ}\text{C}$  (or  $\geq 100.4^{\circ}\text{F}$ ). If more than 1 temperature was taken for a subject on the same day, the highest temperature will be recorded in the e-diary.

Fever will be classified for a given day based on the following scale:

- =., if temperature is missing, or otherwise unavailable.
- =0 (absent), if temperature is not missing and  $< 38.0^{\circ}\text{C}$  ( $100.4^{\circ}\text{F}$ ).
- =1, if temperature is  $\geq 38.0^{\circ}\text{C}$  ( $100.4^{\circ}\text{F}$ ) and  $\leq 38.4^{\circ}\text{C}$  ( $101.1^{\circ}\text{F}$ ).
- =2, if temperature is  $\geq 38.5^{\circ}\text{C}$  ( $101.2^{\circ}\text{F}$ ) and  $\leq 38.9^{\circ}\text{C}$  ( $102.0^{\circ}\text{F}$ ).
- =3, if temperature is  $\geq 39.0^{\circ}\text{C}$  ( $102.1^{\circ}\text{F}$ ) and  $\leq 40.0^{\circ}\text{C}$  ( $104.0^{\circ}\text{F}$ ).
- =4, if temperature is  $> 40.0^{\circ}\text{C}$  ( $104.0^{\circ}\text{F}$ ).

Each category of fever will be included as a separate event in summaries of systemic events.

Similar to the derivations specified for local reactions ([Section 3.5.2.1](#)), fever each day and duration of fever will be derived. However, "each day" and "duration" will be limited to temperature  $\geq 38.0^{\circ}\text{C}$  [ $\geq 100.4^{\circ}\text{F}$ ] only.

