### Reporting Results:

The number, proportion, and corresponding 95% CI will be presented for each vaccine group for each infant dose and the toddler dose.

Local reactions and systemic events that persist beyond Day 7 will be listed.

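### Reactions with no obtainable stop date lose their duration although the diary gives a minimum, and the first-to-last span counts reaction-free days

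*SAP*

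**What the plan says.** SAP 3.5.2.1, in the text after Table 6, counts duration in days "from the start of the first reported reaction to resolution of the last reported reaction, inclusive", that is, end date minus start date plus 1. The end is taken from the diary, "or the date the reaction ended if it continued beyond Day 7". A parenthesis appears to extend the same treatment to diaries that stop before Day 7. If neither source gives an end, the rule is: "If there is no known date on which the reaction ended, then duration will be missing". No minimum, censoring flag or count is specified, and nothing is said about days without the reaction inside the span.

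SAP 3.5.2.2.2 adopts the approach for fever: "fever each day and duration of fever will be derived", restricted to temperatures of at least 38.0°C.

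The protocol tries to prevent unknown end dates. Under Protocol 7.1.1 the site must contact the parent "in order to obtain stop dates for any ongoing local reactions or systemic events on the last day that the e-diary was completed", and adds: "The stop dates should be documented in the source documents and the information entered in the CRF". The visit procedures give a second opportunity, for example at Visit 2: "Review the subject's e-diary data and follow up on any ongoing local reactions or systemic events". On reporting, SAP 6.1 states: "Local reactions and systemic events that persist beyond Day 7 will be listed".

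**The concern.** There are two separate issues.

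The first is the missing-value rule. A reaction that ends within the completed diary needs no outside information. A stop date must be obtained from the parent only when the reaction is still present at the last entry. Durations set to missing therefore come from a group that probably contains more long reactions than the rest, and dropping them may pull the summary down. The plan also discards a known fact, since the diary shows that the reaction lasted at least from its start to the last day reported present.

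The second is the span. Two short episodes separated by clear days become one long duration. No variable for the number of days present is defined, although the daily data are collected.

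What is at stake is the accuracy of a descriptive duration summary within the safety profile, which the primary objective sets out to describe. No hypothesis test or decision rule depends on it.

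**Working it through.** The documents give no figure for duration, so there is none to reproduce. I applied the SAP rule to constructed diaries and then explored the size of the loss under stated assumptions.

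**Step 1. The rule applied to single diaries** (duration = end − start + 1; missing if the end is unknown)

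| Diary | Days present | SAP duration |
|---|---|---|
| Days 1–3, unbroken | 3 | 3 − 1 + 1 = 3 |
| Days 1 and 7 only, resolved | 2 | 7 − 1 + 1 = 7 |
| Days 1, 2 and 6 | 3 | 6 − 1 + 1 = 6 |
| Days 1–7, stop date Day 10 | 7 in diary | 10 − 1 + 1 = 10, retained |
| Days 1–7, stop date unknown | 7 in diary | missing; known minimum 7 |
| Day 7 only, stop date unknown | 1 in diary | missing; known minimum 1 |
| Diary stops on Day 2 with reaction present, stop date unknown | 2 in diary | missing; known minimum 2 |

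The second and third rows follow from the formula alone. The fourth shows that a long reaction with a known end keeps its full length. The last two show that a lost reaction may be short.

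**Step 2. Effect of the missing rule on a mean**

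Assumptions, none of them in the documents: onset on Day 1, unbroken reactions, and geometric durations with daily continuation probability q. A share u of reactions present on Day 7 has no stop date.

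- True mean: 1/(1 − q)
- Share present on Day 7: q^6
- Mean duration of those reactions: 6 + 1/(1 − q)
- Mean of non-missing durations: [1/(1 − q) − u·q^6·(6 + 1/(1 − q))] / (1 − u·q^6)

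Worked case, q = 0.7 and u = 0.5: q^6 = 0.1176 and the mean of those present on Day 7 is 9.333. This gives (3.333 − 0.5 × 0.1176 × 9.333)/(1 − 0.0588) = 2.784/0.9412 = 2.96.

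| q | True mean (days) | Present on Day 7 | u = 0 | u = 10% | u = 50% | u = 100% |
|---|---|---|---|---|---|---|
| 0.5 | 2.00 | 1.6% | 2.00 | 1.99 | 1.95 | 1.91 |
| 0.7 | 3.33 | 11.8% | 3.33 | 3.26 | 2.96 | 2.53 |
| 0.8 | 5.00 | 26.2% | 5.00 | 4.84 | 4.10 | 2.87 |

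The loss is nil when every stop date is obtained and negligible when reactions are short. It is material only if reactions are long and many stop dates are not obtained.

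**Step 3. Whether other planned output makes up for it**

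- The missing reactogenicity summary in SAP 5.3.2 treats a child with any diary day as nonmissing, so a lost duration is not counted there.
- The listing of events beyond Day 7 shows individual cases but does not correct a group summary. It does not clearly cover diaries that stop early with the reaction ongoing.
- SAP section 6 sets out no dedicated duration analysis. SAP 6.3.3, under e-diary completion, refers to the variables of Section 3.5.2, which may be a slip for 3.4.2. Read literally, it would give durations the default statistics of SAP 5.2: n, mean, median, standard deviation, minimum and maximum.

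**The case against.** The strongest reply is that the plan already handles most of this. Sites are obliged to seek stop dates, ongoing events are followed up again at the next visit, and events past Day 7 are listed. Duration is not named among the primary endpoints, which are incidences. Under Table 6 a child with a reported reaction counts as having the reaction whether or not its duration is known. A first-to-last span is also a legitimate, clearly defined quantity, and the diary cannot show whether a second febrile day is a new episode.

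Most of this stands, and it limits the point. A reader might infer that long reactions as a class drop out. They do not, because only those with no obtainable stop date are lost. A reader might also infer that the loss would be invisible. That is not so either: if duration is summarised with n, comparing n with the number of children who had the reaction shows the shortfall, and the each-day values distinguish a Day 1 and Day 7 pattern from a continuous one.

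The reply does not remove the residual problem. The SAP's own rule anticipates that some stop dates will stay unknown. Follow-up visits fall 28 to 42 days after vaccination and so rely on recall. When a stop date is unknown, the plan discards a minimum duration that it holds. The span is well defined, but without days present beside it a reader can take it for continuous duration.

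**Conclusion.** The point holds as a minor weakness in a descriptive summary. The gap-counting effect is certain from the formula: up to 7 days recorded with 2 days present, within one diary week. The missing-value effect is probable in direction but unknown in size. Under the assumptions above it runs from nothing (all stop dates obtained) to a mean of 2.87 against 5.00 (none obtained, long reactions), and the documents do not say where in that range the trial would fall. Lost reactions can also be short, with late onset or an early-stopping diary, so even the direction rests on the judgement that reactions present at the last entry tend to be longer.

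The two effects push in opposite directions but act on different children, so they cannot be assumed to cancel. The documents do not support the inference that the primary safety results are biased: the 7-day incidences, adverse events and serious adverse events do not use duration.

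**What to change.** Amend SAP 3.5.2.1 and 3.5.2.2.2 as follows.

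1. For a reaction with no stop date, derive the minimum duration as last day reported present − start day + 1, flag it as censored (for example ≥7 days), and give the number of such reactions per vaccine group and dose. Summarise duration by median and range or by categories. Do not enter the minimum into a mean as if it were observed. Where censored minima fall below the median, as with onset on Day 7, categories with a separate censored row are safer.
2. Report the number of diary days on which the event was present beside the first-to-last span.

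It would also help to state in SAP section 6 which table carries duration.

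The data are already collected, so the cost is SAP wording, minor programming, one extra column and a censoring footnote per table.

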### 3.5.2.2. Systemic Events and Fever

The systemic events reported in the e-diary after each vaccination are loss of or decreased appetite, drowsiness, and irritability. These will be recorded as present or absent.

#### 3.5.2.2.1. Systemic Events

The presence of systemic events will be recorded in the e-diary daily for 7 days (Day 1 to Day 7) after each vaccination, using the grading scale in Table 7.

**Table 7. Systemic Event Grading Scale**

Systemic Events	GRADE 1 Mild	GRADE 2 Moderate	GRADE 3 Severe
Decreased appetite (loss of appetite)	Decreased interest in eating	Decreased oral intake	Refusal to feed
Drowsiness (increased sleep)	Increased or prolonged sleeping bouts	Slightly subdued; interfering with daily activity	Disabling; not interested in usual daily activity
Irritability (fussiness) (synonymous with restless sleep; decreased sleep)	Easily consolable	Requiring increased attention	Inconsolable; crying cannot be comforted

For decreased appetite or loss of appetite on each day, an indicator variable will be created for decreased appetite on each day, using the following algorithm:

= missing, if decreased appetite is missing.

=0 (none), if no loss of appetite.

=1 (mild), if decreased interest in eating.

=2 (moderate), if decreased oral intake.

=3 (severe), if refusal to feed.

For drowsiness (synonymous with increased sleep) on each day, an indicator variable will be created for drowsiness on each day, using the following algorithm:

= missing, if increased sleep is missing.

=0 (none), if no synonym with increased sleep.

=1 (mild), if increased or prolonged sleeping bouts.

=2 (moderate), if slightly subdued; interfering with daily activity.

=3 (severe), if disabling; not interested in usual daily activity.

For irritability (fussiness, synonymous with restless sleep; decreased sleep) on each day, an indicator variable will be created for irritability on each day, using the following algorithm:

= missing, if irritability is missing.

=0 (none), if no fussiness.

=1 (mild), if easily consolable.

=2 (moderate), if requiring increased attention.

=3 (severe), if inconsolable; crying that cannot be comforted.

For the systemic events, 3 more derivations are required: whether or not a specific reaction occurs on “any day”, whether or not the subject experiences “any systemic event” on a given day, and whether or not the subject experiences “any systemic event” on any day.

Algorithms similar to those described in [Section 3.5.2.1](#) will be used.

### 3.5.2.2.2. Fever

The subject's axillary temperature will be recorded in the e-diary for 7 days (Day 1 to Day 7) after each vaccination. The protocol defines fever as a temperature  $\geq 38.0^{\circ}\text{C}$  (or  $\geq 100.4^{\circ}\text{F}$ ). If more than 1 temperature was taken for a subject on the same day, the highest temperature will be recorded in the e-diary.

Fever will be classified for a given day based on the following scale:

- =., if temperature is missing, or otherwise unavailable.
- =0 (absent), if temperature is not missing and  $< 38.0^{\circ}\text{C}$  ( $100.4^{\circ}\text{F}$ ).
- =1, if temperature is  $\geq 38.0^{\circ}\text{C}$  ( $100.4^{\circ}\text{F}$ ) and  $\leq 38.4^{\circ}\text{C}$  ( $101.1^{\circ}\text{F}$ ).
- =2, if temperature is  $\geq 38.5^{\circ}\text{C}$  ( $101.2^{\circ}\text{F}$ ) and  $\leq 38.9^{\circ}\text{C}$  ( $102.0^{\circ}\text{F}$ ).
- =3, if temperature is  $\geq 39.0^{\circ}\text{C}$  ( $102.1^{\circ}\text{F}$ ) and  $\leq 40.0^{\circ}\text{C}$  ( $104.0^{\circ}\text{F}$ ).
- =4, if temperature is  $> 40.0^{\circ}\text{C}$  ( $104.0^{\circ}\text{F}$ ).

Each category of fever will be included as a separate event in summaries of systemic events.

Similar to the derivations specified for local reactions ([Section 3.5.2.1](#)), fever each day and duration of fever will be derived. However, "each day" and "duration" will be limited to temperature  $\geq 38.0^{\circ}\text{C}$  [ $\geq 100.4^{\circ}\text{F}$ ] only.

## 4. ANALYSIS POPULATIONS

Each subject will be assessed to determine if he or she meets the criteria for inclusion in each analysis population. Classifications will be documented per standard operating procedures. Assessment of subject inclusion in the infant populations may be completed before all toddler-dose procedures are completed.

### 4.1. Evaluable Analysis Populations

The evaluable immunogenicity population will be defined for the 3-dose infant series and the toddler dose separately.

The infant evaluable immunogenicity population will include all subjects who:

1. met all eligibility criteria,
2. were aged 6 weeks (42 to 72 days, inclusive) at the time of the first vaccination,
3. have received 3 doses of vaccine that was randomly assigned to them,

4. have post–Dose 3 blood drawn within 27 to 56 days, inclusive, after the third vaccination,
5. have at least 1 valid and determinate post–Dose 3 assay result, and
6. have no other major protocol violations.

The toddler evaluable immunogenicity population will include all subjects who:

1. met all eligibility criteria,
2. have received 3 doses in the infant series and 1 toddler dose of randomly assigned vaccine,
3. have post–Dose 4 blood drawn within 27 to 56 days, inclusive, after the fourth vaccination,
4. have at least 1 valid and determinate post–Dose 4 assay result, and
5. have no other major protocol violations.

The infant and toddler evaluable immunogenicity populations will be the primary immunogenicity populations for the infant and toddler analyses.

#### **4.2. All-Available Immunogenicity Populations**

The all-available immunogenicity population will be defined for the 3-dose infant series and the toddler dose separately.

The infant all-available immunogenicity population will include all subjects who have at least 1 valid and determinate assay result after Dose 3. The toddler all-available immunogenicity population will include all subjects who have at least 1 valid and determinate assay result after Dose 4.

#### **4.3. Safety Analysis Populations**

Separate safety populations will be defined for the infant series and the toddler dose. Each safety population will include all subjects who receive at least 1 dose of the investigational product for the indicated regimen. In each population subjects will be assigned to the vaccine actually received. If a subject receives different vaccines at different time points, then local reactions, systemic events, and AEs immediately following the vaccination will be assigned to the vaccine most recently received. Compilation of AEs or SAEs from the first infant dose up to the toddler dose will be assigned to the vaccine received. However, subjects who receive both vaccines during the infant series will be assigned to their randomized vaccine group for this compilation of AEs or SAEs.

Subjects who lack any safety data for a particular vaccination will be excluded from analysis.

Subjects vaccinated but not randomized will be included in the safety population for safety analysis. The results from these subjects will be reported under the group corresponding to the vaccine they actually received.

#### 4.4. Other Populations

Not applicable.

### 5. GENERAL METHODOLOGY AND CONVENTIONS

#### 5.1. Hypotheses and Decision Rules

No formal statistical hypothesis test will be performed. There are also no formal statistical decision rules for this study and a descriptive estimation approach will be used to assess all study objectives regarding safety and immunogenicity in the study.

Point estimates and nominal 95% confidence intervals (CIs) will be provided for all safety and immunogenicity endpoints at each planned analysis.

No formal multiplicity adjustments will be applied due to multiple endpoints or multiple looks of the same endpoint.

